schedule:  Arm G: 200 mg b.i.d. x 7 consecutive days every 4 weeks  Arm H: 300 mg q.d. x 7 consecutive days every 4 weeks	s
Arm H: 300 mg q.d. x 7 consecutive days every 4 weeks	
Arm I: 100 mg a d v 5 consecutive days per week for 2 weeks every 4 weeks	
Min 1. 100 mg q.a. x 3 consecutive days per week for 2 weeks every 4 weeks	
Treatment will continue until: clinically significant progressive disease; lack of efficacy; unacceptable toxicity; patient withdrawal of consent; investigator's discretion that it is in the best interest of the patient to withdraw; intercurrent illnes or changes in patient's condition that renders patient ineligible, or continuing treatment of sapacitabine unsafe, or regular follow-up impossible; non-compliance with study medication or protocol-required evaluations and follow-up; or termination of the clinical trial by the sponsor.	
Efficacy Assessment  The primary efficacy endpoint of Part 1, 3 and 4 is the rate of 1-year survival; the primary efficacy endpoints of Part 2 are the rate of clinical benefit (CR, CRp, PR major HI or SD) and the rate of complete response (CR or CRp).	
Safety Assessment  Patients will be seen in the clinic prior to each treatment cycle and monitored by physical exams, laboratory tests, and other appropriate studies. A post-treatment follow-up visit in clinic or by phone will be conducted within 4 weeks after the las dose of the study drug, or prior to the initiation of new cancer treatment if possible	
Study Period December 2007 to November 2011	

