### 3.4. Study Duration

Approximately 100 patients with AML and 60 patients with MDS will be enrolled in Part 1 of this study. Approximately 36 patients with AML will be enrolled in Part 2 of the study. Approximately 60 patients with AML preceded by MDS and 60 patients with MDS will be enrolled in Part 3 and Part 4 of this study, respectively. The patient accrual is projected to be 8 patients per month for approximately 41 months. The study may be closed approximately 6 months after the last patient was enrolled, thus the projected entire study duration is 47 months. After study closure, all patients who are deriving clinical benefit and continue to meet the eligibility criteria may be offered the option to continue treatment on an extension study.

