### 4.3. Removal of Patients from Therapy

Patients have the right to withdraw from the study at any time for any reason. The investigator has the right to withdraw patients from the study according to his/her discretion. When a patient discontinues treatment early, every effort will be made to conduct a post-treatment follow-up visit within 4 weeks after the last dose of study drug or prior to the initiation of new treatment. This post-treatment evaluation may be conducted over the phone if the patient is unable to return to the clinic. The reason(s) for withdrawal must be recorded.

Criteria for terminating participation in the study are listed below:

- Clinically significant progressive disease defined as > 50% increase in the percentage of blasts in bone marrow or peripheral blood over baseline to reach at least 20% blasts in bone marrow or peripheral blood by two assessments while on treatment with an adequate dose
- Lack of efficacy refers to treating physician's judgment that patients are unlikely to benefit from continuation of treatment despite not meeting the criterion of clinically significant progressive disease.
- Unacceptable toxicity
- Patient withdrawal of consent for treatment
- Investigator's discretion that it is in the best interest of the patient to withdraw
- Intercurrent illness: a condition, injury, or disease unrelated to cancer in the opinion of the investigator, that renders continuing sapacitabine treatment unsafe or regular follow-up impossible

- General or specific changes in the patient's condition that renders the patient ineligible for further treatment
- Noncompliance with study medication or protocol-required evaluations and followup visits
- Termination of the clinical trial by the sponsor

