### 6.4. Post-Treatment Follow-up

All patients should be followed regularly until the resolution or stabilization of drug-related toxicity or the start of another anti-cancer treatment. Every effort will be made to conduct a post-treatment follow-up visit within 4 weeks after the last dose of the study drug or prior to the initiation of new treatment, whichever comes first. This post-treatment evaluation may be conducted over the telephone if the patient is unable to return to the clinic.

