g: These evaluations on Day 1 Cycle 1 may not need to be performed if the same evaluations performed during Pre-Study period are within 7 days of the first dose of the study drug; physical exam in clinic may be waived every 1-2 cycles at the investigator's discretion after cycle 6.

h: To be performed prior to the start of cycle 2 on patients who have >5% blasts in bone marrow, i.e., during Day -21-28 of Cycle 1 which may be delayed up to Day 35 for recovery of blood counts; as clinically indicated after subsequent cycles e.g., at the time when blood counts have recovered or worsened.

i: Within 28 days after the last dose of study drug if possible or prior to the initiation of new anticancer treatment, whichever comes first.

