#### 9. EFFICACY ASSESSMENT

The primary efficacy endpoint of Part 1 of this study is 1-year survival, i.e., the proportion of patients who are alive at 1-year measured from the date of the randomization. Secondary efficacy endpoints are the rate of CR, CRp, PR or CRi or hematological improvement and their corresponding durations, transfusion requirements and number of hospitalized days. The primary efficacy endpoints of Part 2 of this study are the rate of clinical benefit response (CR, CRp, PR, or major HI) and the rate of complete response (CR or CRp). Secondary efficacy endpoints are response durations, transfusion requirements, number of hospitalized days, and overall survival. The primary efficacy endpoint of Part 3 and 4 of this study is 1-year survival rate. Secondary efficacy endpoints are the rate of clinical benefit response (CR, CRp, PR, major HI or SD) and their corresponding durations, transfusion requirements, number of hospitalized days and overall survival.

The tissue samples supporting the diagnosis of AML or MDS, and the responses to sapacitabine may be submitted for central review.

Table 6 Response Criteria

Passansa Description					
Response	Description				
Complete Remission (CR) 	Normalization of peripheral neutrophils to ≥1000 /µL, platelet to ≥100,000/µL within 2 weeks of bone marrow biopsy/aspirate, and bone marrow to ≤5 % blasts; independent of transfusions*; and no extramedullary leukemia.				
Complete remission with incomplete platelet count recovery (CRp) 	Normalization of bone marrow to $\leq$ 5% blasts; peripheral neutrophils $\geq$ 1000 /µl, platelet $<$ 100,000 /µL within 2 weeks of bone marrow biopsy/aspirate; independent of transfusions*; and no extramedullary leukemia.				
Complete remission with incomplete blood count recovery (CRi) 8	Normalization of bone marrow to $\leq$ 5% blasts; peripheral neutrophils $<1000~/\mu$ L, platelet $<100,000/\mu$ L within 2 weeks of bone marrow biopsy/aspirate; independent of transfusions *; and no extramedullary leukemia.				
Partial Remission (PR) 8	Normalization of peripheral neutrophils to $\geq 1000 \ / \mu L$ , platelet to $\geq 100,000/\mu L$ within 2 weeks of bone marrow biopsy/aspirate, $\geq 50\%$ decrease in bone marrow blasts over pretreatment but still >5%; independent of transfusions * .				
Hematological improvement (HI) 9	Major response:				

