#### 11.3. Sample Size for Part 3 and 4

The primary objective of Part 3 and 4 of the study is to evaluate 1-year survival rate of 3 dosing schedules in elderly patients with previously untreated AML which evolved from MDS after receiving hypomethylating agents for the MDS or older patients with previously treated MDS; the secondary objectives are to assess the number of patients who have achieved a CR, CRp, PR, major HI or SD and their corresponding durations, transfusion requirements, number of hospitalized days and safety.

The primary efficacy endpoint is 1-year survival measured from the date of randomization. Statistically, the purpose of the trial is to reject the dosing schedules from further study if they were insufficiently active based on the rate of clinical benefit response and to accept them for further study if they were truly active. For "screening" purpose, a Bayesian continuous futility monitoring rule is used for each dose schedule separately based on the rate of clinical benefit response, and a "selection" design to choose the better dosing schedule based on 1-year survival rate if all 3 dosing schedules are found to have activity based on the rate of clinical benefit response. This randomized phase II trial is not expected to have sufficient power to compare the 3 dosing regimens on the basis of 1-year survival rate.

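### Section 3.4 projects closure about 6 months after last enrolment, but the primary endpoint of Parts 1, 3 and 4 is survival at 1 year, and no vital-status contact to month 12 is required off drug or after closure

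*Combined protocol and SAP*

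**What the plan says.** **Closure.** Section 3.4 projects 8 patients a month for about 41 months and then says: "The study may be closed approximately 6 months after the last patient was enrolled, thus the projected entire study duration is 47 months". The synopsis gives matching dates: "Study Period December 2007 to November 2011". After closure, patients still deriving benefit may be offered an extension study. No collection of survival status is described for that study or for anyone else after closure.

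**Endpoint.** Section 9 defines the Part 1 primary endpoint as "the proportion of patients who are alive at 1-year measured from the date of the randomization". For Parts 3 and 4, Section 11.3 says: "The primary efficacy endpoint is 1-year survival measured from the date of randomization". Sections 11.1.2 and 11.3.2 then choose the schedule with the better observed 1-year rate. They state a probability above 80% of choosing correctly between true rates of 45% and 30% with 20 patients per arm.

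**Follow-up on drug.** The synopsis says: "Patients will be seen in the clinic prior to each treatment cycle and monitored by physical exams". Vital status is therefore known until closure for patients still on treatment.

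**Follow-up off drug.** Section 6.4 has patients followed regularly until drug-related toxicity resolves or stabilises, or another anti-cancer treatment starts. It also asks for one "follow-up visit within 4 weeks after the last dose of the study drug or prior to the initiation of new treatment", by telephone if necessary. Section 4.3 agrees, and Table 5, footnote i, sets the last column of the calendar at: "Within 28 days after the last dose of study drug if possible or prior to the initiation of new anticancer treatment, whichever comes first". Table 5 has no survival contact.

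**Analysis.** Section 11.4 reports the 1-year rate with a 95% confidence interval and names Kaplan-Meier for response durations and overall survival. The next sentence censors patients who leave the study for reasons other than progression at their last response assessment. No rule covers a patient whose 1-year status is unknown.

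**The concern.** A proportion alive at 1 year can be observed directly only if every randomized patient has vital status to month 12. The projected closure date stops observation of the last entrants between 6 and 12 months. Separately, a patient in Parts 1, 3 or 4 who stops drug before month 12 may have no required contact once toxicity has settled or new therapy has begun, whenever that patient was enrolled.

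Two things are at stake. The deliverable of Parts 1, 3 and 4 is an estimated 1-year rate per schedule with its interval, and some of the outcomes behind it would be missing by design. How those unknowns are treated would also affect which schedule is selected, and the plan does not say how they are treated.

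**Working it through.** **Inputs.** Section 3.4: 8 patients a month, 41 months of accrual, closure 6 months later; part sizes 100 + 60 + 36 + 60 + 60 = 316. Synopsis: about 325 patients. Sections 11.1.2 and 11.3.2: 45% against 30%, 20 per arm.

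**1. The plan's own figures.** Duration: 41 + 6 = 47 months, and December 2007 plus 47 months is November 2011. Accrual: 8 × 41 = 328, close to 325. Selection probability, exact binomial with 20 per arm, 45% against 30%: 0.836 with ties split at random (0.796 with ties counted as failures). With ties split, the stated figure of better than 80% is reproduced.

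**2. Patients under 12 months from entry at closure.** 8 × 6 = 48, or 48/325 = 14.8%, over all parts. The last enrolment falls at month 41 (about May 2011). Twelve months of follow-up for that patient ends at 41 + 12 = 53 months (about May 2012).

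**3. How many are alive with status unobserved.** Assume exponential survival with hazard h = −ln(S₁) per year, and even entry over the last 6 months of accrual, so that follow-up at closure is uniform on 0.5 to 1 year. Then

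P(alive at closure) = [exp(−0.5h) − exp(−h)] / (0.5h).

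- S₁ = 0.30: 0.412, and 48 × 0.412 = 19.8 patients.
- S₁ = 0.45: 0.553, and 48 × 0.553 = 26.5 patients.

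So about 20 to 27 patients, fewer if the extension study records their status.

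**4. Late entrants per arm.** The plan does not split late entry by part, so two cases bracket it.

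- Spread in proportion: 20 × 48/316 = 3.04, about 3 per arm.
- All in Parts 3 and 4 (an assumption, but possible because 120/8 = 15 months of accrual): 48/6 = 8 per arm.

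**5. Probability of correct selection, 45% against 30%, 20 per arm, ties split.** Complete data give 0.836. The values below are simulated (exponential survival, late entrants censored uniformly at 6 to 12 months), except the last row, which is exact binomial with 20 − 8 = 12 per arm.

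| Handling of unknown 1-year status | 3 late per arm | 8 late per arm |
|---|---|---|
| Kaplan-Meier | 0.83 | 0.82 |
| Counted as alive | 0.83 | 0.83 |
| Unknowns alone left out | 0.83 | 0.81 |
| Counted as dead | 0.82 | 0.775 |
| All late entrants left out | not calculated | 0.775 |

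**6. Effect on the estimate itself.** Take an arm with a true rate of 45%.

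- 8 of 20 late: the expected observed rate is 0.6 × 0.45 = 27% if unknowns count as not alive, and 0.27 + 0.4 × 0.553 = 49% if they count as alive.
- 3 of 20 late: 0.85 × 0.45 = 38% and 0.3825 + 0.15 × 0.553 = 47%.

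In the 8-per-arm case the low end lies below the 30% that the plan assigns to the worse schedule.

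**The case against.** Several points on the other side are sound.

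- **Closure is permissive.** Section 3.4 says the study may close at about 6 months. A reader might infer that the protocol mandates closure before the endpoint matures, and it does not. It does, however, build that closure into its projected duration and dates.
- **Off-drug follow-up can exceed 28 days.** A reader might infer from Table 5 that nothing happens after the 4-week visit. Section 6.4 provides regular follow-up until toxicity settles or new treatment starts. Section 8.1 follows drug-related events on similar terms, and Section 8.2 requires reporting of deaths in patients who are off drug but still on study. None of these runs to month 12 by requirement.
- **Survival is obtained in practice.** Section 3.3 reports 7 Arm A patients who lived at least 1 year, and overall survival has a planned analysis. This shows that collection is feasible. It does not show that it is complete or continues after closure. The Operations Manual is not among the documents, and the protocol does not cite it for survival follow-up.
- **Selection is robust.** A reader might infer that the 80% claim fails. Under Kaplan-Meier, the only survival method Section 11.4 names, it holds with either 3 or 8 late entrants per arm. The plan proposes neither of the rules that bring it below 0.80, and it disclaims power and formal testing for 1-year survival.
- **The 48 is not a count of lost primary endpoints.** It can include Part 2 patients, who have no 1-year endpoint.
- **The censoring sentence fits response duration.** A reader might take it as governing survival because it directly follows the mention of overall survival. The text does not settle this, so it needs only clarification.

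What remains is that no provision secures 1-year status for every patient randomized in Parts 1, 3 and 4, and that Kaplan-Meier is not assigned to the 1-year proportion.

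**Conclusion.** The concern holds as one of endpoint ascertainment. If the projected plan is followed, about 48 patients over all parts would be under 12 months from entry at closure. About 20 to 27 of them would be alive with 1-year status unobserved in this study, assuming exponential survival at 30% to 45% and even accrual at 8 a month. How many of these fall in Parts 1, 3 and 4 cannot be read from the documents. The off-drug gap is additional, and its size cannot be estimated from them.

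Late entry alone does not overturn the stated selection probability if Kaplan-Meier is used: 0.83 with 3 late entrants per arm and 0.82 with 8, against 0.84 with complete data. Of the cases examined, it drops below 80%, to about 0.77 to 0.78, only with 8 late entrants per arm and either unknowns counted as dead or all late entrants left out. The plan should be changed because its primary endpoint would be incompletely observed and the handling of unknowns is unstated. A demonstrated failure of the selection design is not the reason.

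**What to change.** - **Sections 3.4 and 6.4, and Table 5.** Require vital status, by phone or from records, for every patient randomized in Parts 1, 3 and 4, on or off drug, until 12 months after the last randomization in those parts. Add this contact as a row in Table 5. Survival follow-up then ends at about month 53 if one of those parts enrols last. Treatment may still close at month 47.
- **Section 11.4.** State that if any 1-year status is missing, the 1-year rate is estimated by Kaplan-Meier with censoring at the date last known alive. State also that censoring at the last response assessment applies to response durations only.

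The text change is a few sentences and one table row. No extra patients or clinic visits are needed. The real cost is the phone or records contacts and about 6 more months of survival follow-up (53 against 47).

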#### 3.5. Criteria for Study Discontinuation

This trial will be monitored by Cyclacel or its designees. The trial may be discontinued for safety concerns, slow accrual, or at the sponsor's discretion.

### 3.6. Maintenance of the Treatment Codes and Procedure for Breaking Codes

This is an open label study. There is no need to break the treatment codes.

### 3.7. Case Report Form as Source Data

The case report form (CRF) pages containing disease assessment by investigator, e.g., CR, CRp, PR, CRi and hematological improvement may serve as the source data for the secondary efficacy endpoints of Part 1, 3 and 4 and primary efficacy endpoints of Part 2 of the study.

#### 3.8. Correlative Study

Analysis of the expression of key proteins that may be involved in the cellular biology and pharmacology of sapacitabine and its major metabolite CNDAC may be performed on bone marrow aspirate or biopsy samples obtained prior to and after the treatment with sapacitabine. The proteins of interest include nucleoside transporters, nucleoside kinases and

deaminases which may be involved in the entry of sapacitabine and CNDAC into cells and their subsequent activation and inactivation inside cells. The purpose of the correlative study is to explore whether there is any correlation between the expression levels of these proteins and clinical response to sapacitabine. The correlative study is optional for patients. Study details will be provided in the Operations Manual.

#### 4. PATIENT SELECTION

Only patients with a diagnosis of AML based on the World Health Organization (WHO) classification , or with a diagnosis of MDS carrying an International Prognostic Scoring System (IPSS) scores of intermediate-2 or high-risk and who meet all inclusion and no exclusion criteria can be considered for enrollment in this study. Only investigators who are listed on the FDA form 1572 are authorized to obtain informed consent. No study-specific procedures can be performed until the potential patient has signed an informed consent form that has been approved by the Institutional Review Board (IRB) or Ethics Committee (EC). Procedures that are performed prior to patient signing an informed consent form can be used to satisfy protocol requirements if these procedures are performed as routine medical care for patient's underlying cancer and other illnesses.

### 4.1. Eligibility Criteria

Patients must fulfill all of the following criteria:

- 4.1.1. For Part 1 of the study, a histologically or pathologically confirmed diagnosis of AML based on WHO classification which is previously untreated by systemic therapy or is in first relapse after achieving a complete remission (CR or CRp) to initial induction, consolidation and/or maintenance therapy; a histologically or pathologically confirmed diagnosis of MDS based on French-American-British (FAB) classification with an IPSS score of intermediate -2 or high - risk which has been previously treated with hypomethylating agents. For Part 2 of the study, a histologically or pathologically confirmed diagnosis of AML based on WHO classification which is previously untreated by systemic therapy in the setting of significant concomitant medical illnesses defined by having a HCTCI of 2 and higher (See Appendix B). For Part 3 of the study, a histologically or pathologically confirmed diagnosis of AML preceded by MDS based on WHO classification after receiving hypomethylating agents for the preceding MDS but the newly diagnosed AML has not been treated with any systemic anti-leukemic therapy. For Part 4 of the study, a histologically or pathologically confirmed diagnosis of MDS based on FAB classification with an IPSS score of intermediate-2 or high- risk and 6 - < 20% blasts in bone marrow which has been previously treated with hypomethylating agents.
- 4.1.2. Age  $\geq 70$  years for AML or  $\geq 60$  years for MDS

- 4.1.3. Eastern Cooperative Oncology Group (ECOG) performance status 0-2 (See Appendix C)
- 4.1.4. Adequate renal function
  - Creatinine  $\leq 1.5 \times ULN$
- 4.1.5. Adequate liver function
  - Total bilirubin or direct bilirubin ≤ 1.5 x ULN
  - Alanine aminotransferase (ALT or SGPT)  $\leq 2.5$  x institutional upper limit of normal (ULN) or  $\leq 5$  x ULN if the liver is involved by leukemia
- 4.1.6. Life expectancy reasonably adequate for evaluating the treatment effect
- 4.1.7. Patient must be able to swallow capsules.
- 4.1.8. Patients must be at least 2 weeks from prior systemic therapy for AML or MDS, radiation therapy, major surgery, or other investigational therapy, and have recovered from clinically significant toxicities of these prior treatments. Patients with ≥ 50,000 WBC in peripheral blood may receive hydroxyurea to control the WBC <50,000 prior to starting sapacitabine if this is considered by the treating physician to be in the best interest of the patient.
- 4.1.9. All men of reproductive potential must agree to practice effective contraception for 4 weeks prior to study entry, during the entire study period and for one month after the study unless documentation of infertility exists.
- 4.1.10. Ability to understand and willingness to sign the informed consent form

